#### 5.6.6.2 Bone Turnover Assessments

For Phase 2 patients in the Bone Turnover Markers Evaluable Set, summary statistics at each protocol visit for BSAP, PINP and CTX will be displayed. Changes from baseline at the 6th week, 12th week and EOT visit will be presented.

All serum bone turnover data will be listed.

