### 3.1.5 Phase 2 Secondary Objectives

The secondary objectives of the Phase 2 portion of this study are to:

- Further characterize the safety of H3B-6545 in this patient population.
- Further characterize the PK of H3B-6545. At least sparse PK samples will be collected from all patients on study.
- Evaluate the effect of a high-fat meal on the relative bioavailability of H3B-6545.
- Assess the effect of H3B-6545 on serum bone turnover markers, namely bone-specific alkaline phosphatase (BSAP), for osteoclast metabolism; amino-terminal propeptide of type 1 collagen (PINP), for bone formation; and C-terminal cross-linking telopeptide of type 1 collagen (CTX), for bone resorption.
- Assess the effect of H3B-6545 on endometrial thickness and uterine volume. This objective will be assessed in a subgroup of women with intact uteri.

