## 3.2 Overall Study Design and Plan

This is a first-in-human, multi-center, open-label, dose-escalation followed by dose expansion Phase 1/2 study of H3B-6545 for women with ER-positive, HER2-negative, locally advanced or metastatic breast cancer. The study contains a Phase 1 dose escalation part, and a Phase 2 dose expansion portion as shown below:

- The Phase 1 dose escalation part will follow a standard 3+3 cohort design to determine the MTD/RP2D. Once a subject has completed Cycle 3 at her assigned dose level of drug, intra-subject dose escalation will be allowed.

- The Phase 2 dose expansion part will examine the efficacy of the RP2D. Two substudies are included to examine the food effect on PK and effect of H3B-6545 on the endometrium. In addition, approximately [REDACTED] subjects having a clonal *ESR1* Y537S mutation, in the absence of *ESR1* D538G mutation are enrolled to examine the efficacy.

Abbreviations: DL=dose level; ER $\alpha$ mut=estrogen receptor alpha mutant; ER $\alpha$ WT=estrogen receptor alpha wild-type; MTD=maximum tolerated dose; PK=pharmacokinetics; PO=orally (by mouth); QD=once daily; RP2D=recommended Phase 2 dose.

All subjects entering this study will receive H3B-6545 PO once daily. Efficacy, safety and PK/PD will be assessed according to the Schedule of Assessments (Protocol Appendix E). Subjects are permitted to continue treatment with H3B-6545 until disease progression, unacceptable toxicity, or decision to discontinue treatment by the subject or the study physician. After discontinuation from protocol treatment, subjects must be followed for adverse events (AEs) for 28 days after their last dose of study drug. If a subject discontinues therapy for a reason other than disease progression, they will continue to be evaluated for response until disease progression or until they start a new anti-cancer therapy. Following disease progression, all subjects will be followed for survival at least every 12 weeks, and survival follow-up will end 6 months after the last subject receives their first dose of study treatment (at the time of data cutoff for the primary analysis) (as of Amendment 9), and no survival follow-up will be done in the Extension Phase.

The primary analysis for efficacy will be based on data collected 6 months after the last subject receives their first dose of study treatment.

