### 5.1.5 Phase 2 Secondary Endpoint(s)

Secondary study endpoints for Phase 2 are:

- Safety/tolerability: same as Phase 1.
- Further characterize PK of H3B-6545.
- Evaluate the effect of a high-fat meal on the relative bioavailability of H3B-6545.
- Endometrial thickness and uterine volume in a subgroup of subjects.
- Effect of H3B-6545 on serum bone turn-over markers, namely BSAP (for osteoclast metabolism), PINP (for bone formation), and CTX (for bone resorption).

[figure not shown]

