- **Bone Turnover Markers Evaluable Set**, which will consist of those subjects who have baseline/screening assessments of bone turnover markers and at least one additional assessment at 6 and/or 12 weeks after starting trial therapy. To be included in this set, subjects must have received trial therapy uninterrupted for at least 14 days prior to 6-week or the 12-week assessment.

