### 5.2.4 Demographic and Other Baseline Characteristics

Demographic and baseline characteristics for the FAS will be summarized by treatment groups using descriptive statistics. Continuous demographic and baseline variables include age (year), weight (kg) and height (cm); categorical variables include age group ( $\geq 18$  to  $<65$ ,  $\geq 65$ ) sex (male, female), race (White, Black or African American, Asian [Japanese, Chinese, Other Asian], American Indian or Alaska Native, Native Hawaiian or other Pacific Islander, and Other), Ethnicity (Hispanic or Latino, Not Hispanic or Latino), Eastern Cooperative Oncology Group Performance Status (ECOG PS), measurable disease at baseline, bone disease without measurable lesion at baseline (defined by subjects without measurable disease and with non-target bone lesion presented at baseline).

Disease history will be summarized by treatment group:

- Time from tumor diagnosis to date of the first dose (months)
- Age at diagnosis (years) summarized both descriptively and by categories ( $<65$ ,  $\geq 65$ )
- Location of primary tumor site
- Tumor staging using TNM classification

Disease characteristics at study entry will be summarized by treatment groups (based on FAS), and baseline *ESR1* mutation groups (based on FAS subjects who started on 450 mg)

- Metastatic sites at baseline

- Mutation status of *ESR1*, *PIK3CA* (phosphatidylinositol-4,5-bisphosphate 3-kinase catalytic subunit alpha), *AKT1* (AKT serine/threonine kinase 1) at baseline
- Progesterone Receptor (PgR) status and positivity as percentage of PgR positive cells at baseline.

Previous anti-cancer medications will be summarized by treatment groups (based on FAS) and baseline *ESR1* mutation groups (based on FAS subjects who started on 450 mg):

- Number of previous anti-cancer regimens containing endocrine therapies in locally advanced/ metastatic disease settings
- Number of previous anti-cancer regimens not containing endocrine therapies in locally advanced/ metastatic disease settings
- Therapeutic setting of previous anti-cancer regimens
- Type of previous anti-cancer regimens (endocrine, including fulvestrant, aromatase inhibitor (AI), tamoxifen and other, CDK4/6 inhibitor, chemotherapy, other; CDK4/6i and AI; CDK4/6i and fulvestrant) in locally advanced/ metastatic disease settings

Previous radiotherapy will be summarized by treatment groups (based on FAS):

- Number of subjects having prior radiotherapy
- Last radiotherapy site

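### Bone turnover marker changes are not shown by baseline bone metastases, so a drug effect on bone cannot be told apart from tumor change in bone, least of all at end of treatment

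*SAP*

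**What the plan says.** SAP section 3.1.5 sets the objective: "Assess the effect of H3B-6545 on serum bone turnover markers", naming BSAP, PINP and CTX. Section 5.1.5 lists the matching secondary endpoint: "Effect of H3B-6545 on serum bone turn-over markers".

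Section 5.2.1 defines the Bone Turnover Markers Evaluable Set as "subjects who have baseline/screening assessments of bone turnover markers and at least one additional assessment at 6 and/or 12 weeks" after the start of therapy. It adds an exposure condition: "subjects must have received trial therapy uninterrupted for at least 14 days prior to 6-week or the 12-week assessment". It sets no condition on bone metastases.

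Section 5.6.6.2 plans summary statistics at each protocol visit and a listing of all the data. On change it says: "Changes from baseline at the 6th week, 12th week and EOT visit will be presented". Sections 5 and 5.6 group results by starting dose. The only safety subgroups named in 5.6 are *ESR1* mutation groups and PgR status. Section 5.3.2 states that covariate adjustment does not apply.

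Bone disease is expected and recorded. Section 5.2.4 tabulates metastatic sites at study entry, and its baseline categories include "bone disease without measurable lesion at baseline (defined by subjects without measurable disease and with non-target bone lesion presented at baseline").

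On the timing of EOT, section 3.2 says: "Subjects are permitted to continue treatment with H3B-6545 until disease progression, unacceptable toxicity, or decision to discontinue treatment".

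**The concern.** BSAP, PINP and CTX are serum measures. They do not show whether the turnover comes from bone free of tumor or from bone around metastases. That these markers can move with tumor in bone is general clinical knowledge; the SAP does not say it. The SAP does describe PINP as a marker of bone formation and CTX as a marker of bone resorption.

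In a single-arm trial, a fall in a table that mixes subjects with and without bone metastases could be a drug effect on bone, tumor response in bone, or both. A rise could likewise be a drug effect or progression in bone. This summary is the only planned answer to a stated secondary objective, so its readability matters even though no test depends on it.

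EOT is the least readable timepoint. Subjects may stay on drug until progression, so an EOT sample may be drawn at or near progression and compared with a pre-treatment value. The 14-day exposure condition, which helps link a marker change to the drug, is tied to the 6-week and 12-week samples and not to EOT.

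**Working it through.** The SAP states no sample size, effect size or precision for the bone marker analysis, so there is no figure to reproduce. The check has two parts.

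**1. Does anything in the SAP separate tumor in bone from a drug effect?**

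| Possible safeguard | Where | Finding |
|---|---|---|
| Restriction of the analysis set | 5.2.1 | Samples and exposure only; nothing on bone metastases |
| Split in the analysis | 5.6.6.2 | None stated |
| Safety subgroups | 5.6 | *ESR1* groups and PgR status only |
| Covariate adjustment | 5.3.2 | Not applicable |
| Control arm | 3.2 | None; open-label escalation and expansion |
| Variable needed for a split | 5.2.4 | Available: metastatic sites at baseline |
| Reason treatment ended | 5.2.2 | Available: primary reason is summarized |

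No readable safeguard exists, and both variables for a split are already collected.

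**2. How large could the mixing be?** All inputs here are assumptions; none is in the SAP. Let *p* be the share of the set with bone metastases (0.40, 0.60 or 0.75), *a* a uniform tumor-driven change in those subjects (-30% or +30%), and the drug effect on bone zero. Then

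overall geometric mean change = (1 + *a*)^*p* - 1.

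| *p* | Response, *a* = -30% | Progression, *a* = +30% |
|---|---|---|
| 0.40 | 0.70^0.40 - 1 = -13.3% | 1.30^0.40 - 1 = +11.1% |
| 0.60 | 0.70^0.60 - 1 = -19.3% | 1.30^0.60 - 1 = +17.0% |
| 0.75 | 0.70^0.75 - 1 = -23.5% | 1.30^0.75 - 1 = +21.7% |

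The SAP summarizes with means and medians, not geometric means. For an arithmetic mean of percentage changes the formula is *p* × *a*, and the result is similar: 0.40 × 30 = 12 and 0.75 × 30 = 22.5 percentage points. With a wider assumed range (share 0.3 to 0.7, shift 20% to 40%), the result runs from 0.3 × 20 = 6 to 0.7 × 40 = 28 percentage points in either direction.

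A uniform shift is the extreme case. If half of the subjects with bone metastases shift by -30% and half by +30%, the geometric mean change is (0.70 × 1.30)^(*p*/2) - 1. This is 0.91^0.20 - 1 = -1.9% at *p* = 0.40 and 0.91^0.375 - 1 = -3.5% at *p* = 0.75. Mixed outcomes largely cancel in the mean, though they still widen the spread.

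**The case against.** The strongest reply is that the plan makes no wrong statement here. Section 5.6.6.2 is descriptive: it has no test, confidence interval, threshold or decision rule. The objective names the markers, and a marker fall caused by drug-induced tumor response is also an effect of the drug on the markers. This stands. A reader might infer that the plan treats tumor response or progression as a drug effect on bone, or that the objective goes unanswered. The SAP supports neither: it prescribes no interpretation and never limits the objective to bone free of tumor.

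A reader might also infer that everyone is pooled into one figure. That is not so, since results are shown by starting dose. Dose grouping does not separate bone involvement, however, and that is the only pooling at issue.

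Much could be recovered later. Marker data and disease characteristics are listed, reasons for discontinuation are summarized, and section 5.8 allows exploratory analyses. This is true, but a split chosen after seeing the data carries less weight than a prespecified one.

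The exploratory subgroup lists in 5.3.4 and 5.6.2.2 are redacted and the protocol is not shown, so a bone-disease split or a sampling restriction elsewhere cannot be excluded. But 5.3.4 opens with efficacy endpoints, the list in 5.6.2.2 sits under adverse event data, and 5.6.6.2 refers to neither.

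On EOT, progression may be at any site, toxicity and subject or physician decision also end treatment, and EOT is a separate timepoint that cannot distort weeks 6 and 12. These limits stand. The SAP gives no figure for how many EOT samples would fall at progression in bone.

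**Conclusion.** The point holds as a cheap, worthwhile improvement to a descriptive secondary analysis. As planned, the changes from baseline cannot distinguish a drug effect on bone from tumor change in bone, and the EOT change is the hardest to read. This conclusion rests on three things: the markers can reflect tumor in bone (clinical knowledge), the set includes subjects with bone metastases (expected from 5.2.4), and there is no control arm (3.2).

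The size is unknown. The range of -13% to -23% or +11% to +22% depends wholly on the assumed uniform 30% shift in 40% to 75% of subjects with no drug effect, and it shrinks to a few percent if response and progression are evenly mixed.

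A reader might go further and conclude that only subjects without bone metastases can answer the objective, or that EOT should be dropped. The SAP does not support that. Its objective covers the whole Phase 2 population, and change in the stratum without bone metastases is still an uncontrolled before-after comparison. That stratum is less affected by tumor in bone; it is not free of other influences.

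**What to change.** In section 5.6.6.2:

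- Keep the planned overall summary by starting dose.
- Add BSAP, PINP and CTX changes from baseline at week 6, week 12 and EOT by presence or absence of bone metastases at baseline, taken from the metastatic-sites variable in 5.2.4.
- Prespecify the stratum without bone metastases as the one less affected by tumor in bone.
- Show EOT changes by whether treatment ended for progression, using the discontinuation reason already summarized under 5.2.2.

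The cost is one more grouping in an existing table and one more for EOT, with no new data. The downside is smaller strata and less precise summaries, especially where starting-dose groups are small.

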#### 5.6.6.3 ECOG PS

ECOG PS will be listed.

#### 5.6.6.4 Other analyses

The following data will be listed:

- Meal questionnaire
- Multiple-gated acquisition (MUGA) or Echocardiogram (Left Ventricular Ejection Fraction, LVEF)
- Pregnancy test

### 5.7 Other Analyses

The effect of a high-fat meal on H3B-6545 PK is analyzed in a separate document. Other analyses may be conducted as appropriate.

### 5.8 Exploratory Analyses

Additional exploratory analyses may be conducted as appropriate. Any exploratory analyses that are performed will be appropriately titled and labeled as exploratory and will be clearly distinguished from planned analyses when results are reported in the CSR.

## 6 INTERIM ANALYSES

There would be an interim analysis to define the MTD and/or RP2D prior to initiating Phase 2 of the study. There would also be an interim analysis to evaluate the effect of a high-fat meal on H3B-6545 PK. Safety data would be provided and reviewed periodically. Database locks are not required to perform these analyses.

CCI

## 7 CHANGES IN THE PLANNED ANALYSES

Major changes to planned analyses in protocol are summarized below:

Change	Rationale	Sections in SAP
CCI		
Definition of prior and concomitant medications	New definition allows medications to be classified into multiple categories, reflecting the complete periods of drug administration.	Section 5.2.5

## 8 DEFINITIONS AND CONVENTIONS FOR DATA HANDLING

Baseline is defined as the last non-missing pre-treatment value (or average value for ECG parameters, when multiple assessments are collected in triplicate at a timepoint) from either a scheduled or an unscheduled assessment.

Pre-treatment assessments: if both date and time are available, a pre-treatment assessment is defined as one that is measured before the date and time of the first dose of study drug. If only date is available and time is missing/not collected, scheduled assessment(s) measured on first dose date of study drug will be considered pre-treatment; unscheduled assessment measured on first dose date will be considered as post-treatment.

On treatment assessments (or assessments during treatment period) are defined as post-baseline assessments from first dose date of study drug to 28 days after the last dose of study drug. End of treatment assessments are those collected at the EOT visit. Safety follow up assessments are those collected at the safety follow up visit. On treatment assessments for end of treatment visit and safety follow up visit will be reported in 'by-timepoint' analysis and included in all abnormality/threshold analysis.

Study Day 1 is defined as the date of the first dose of study drug administered.

If there are multiple values reported for an assessment at a specific visit/timepoint, the average value will be calculated and used in summary tables and figures. Both original values and averages will be displayed in subject data listings.

All by-visit analyses will be performed using assessments at corresponding scheduled visits (including EOT and safety follow-up visits). A scheduled visit will be included in summary tables when there are  $\geq 10\%$  subjects (based on number of subjects dosed) having non-missing assessment at the visit. For shift tables, all post-baseline assessments including those collected at scheduled and unscheduled visits will be used.

Further definitions and conventions for data handling will be presented in “Programming Specifications”.

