#### 5.6.5.2 Central and Local 12-lead ECG Data

In addition, central triplicate 12-lead ECG are collected at screening, and on Day 1 and Day 15 of Cycle 1 (for Phase 2 subjects), Day 1 of Cycle 2, 3, and 4 (predose and 3 hours postdose), as well as at the End of Treatment (EOT) visit.

Local 12-lead ECG data maybe collected at scheduled visits starting from Cycle 5 until the last cycle prior to the EOT visit, and at unscheduled visits as clinically required.

For each ECG parameter (QTcF, PR, etc), the average of triplicate at each timepoint (screening, predose and post dose on Day 1 of Cycle 1, 2, 3, 4, EOT, unscheduled, etc) will be used in ECG analysis below:

- By-timepoint analysis: ECG parameters numerical results and changes from baseline at each scheduled timepoint (including EOT and safety follow up visit) during the treatment period will be summarized by treatment groups.
- Categorical analysis: the number (percentage) of subjects who meet the following criterion with at least 1 post-baseline ECG result during the treatment period will be summarized (based on worst post-baseline results) and presented by treatment groups:

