**Table 5 Criteria for Categorical Analysis of ECG Parameters**

ECG parameter	Criteria
QTcF	> 450 and $\leq$ 480 msec
	> 480 and $\leq$ 500 msec
	> 500 msec
	Change from baseline > 30 and $\leq$ 60 msec
	Change from baseline > 60 msec
	> 500 msec or change from baseline > 60 msec
PR	Change-from-baseline > 25% resulting in PR > 200 msec
QRS	Change-from-baseline > 25% resulting in QRS > 120 msec
HR	Changes reflecting a more than 25% decrease from baseline to a HR < 50 bpm
	Changes reflecting a more than 25% decrease from baseline to a HR < 40 bpm
	Changes reflecting a more than 25% increase from baseline to a HR > 100 bpm

HR = heart rate, QTcF = QT interval corrected for heart rate using Fridericia's formula.

Shift tables will present changes in ECG interpretation (categorized as normal; abnormal, not clinically significant; and abnormal, clinically significant) from baseline to worst post-baseline reading; if multiple interpretation records are collected in triplicate on Day 1 predose, the worst interpretation (eg, abnormal is worse than normal) prior to the first dose will be used as baseline interpretation.

All ECG data, including 24 hour continuous Holter ECG, central and local 12-lead ECG data will be listed. All ECG abnormalities based on central/local 12-lead ECG will also be listed.

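### Section 8 treats any untimed scheduled assessment on the first dose date as pre-treatment, so an untimed post-dose Cycle 1 Day 1 ECG could serve as, or confuse, the numeric ECG baseline

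*SAP*

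**What the plan says.** SAP Section 8 sets the general convention: "Baseline is defined as the last non-missing pre-treatment value", with triplicate ECG readings averaged, and scheduled and unscheduled assessments both eligible. What counts as pre-treatment depends on whether a clock time exists:

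- With a time: pre-treatment only if taken earlier than the moment of first dosing.
- Without a time, scheduled: "scheduled assessment(s) measured on first dose date of study drug will be considered pre-treatment".
- Without a time, unscheduled: "unscheduled assessment measured on first dose date will be considered as post-treatment".

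Section 5.6.5.2 describes central triplicate ECGs at screening, on Days 1 and 15 of Cycle 1 for Phase 2 subjects, on "Day 1 of Cycle 2, 3, and 4 (predose and 3 hours postdose"), and at end of treatment. It then lists the timepoints at which triplicates are averaged: "screening, predose and post dose on Day 1 of Cycle 1, 2, 3, 4, EOT, unscheduled, etc".

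Table 5 uses the baseline in several rows, among them "Change from baseline > 60 msec" for QTcF and "Changes reflecting a more than 25% decrease from baseline to a HR < 50 bpm" for heart rate. PR and QRS each have a 25% change criterion. The text under Table 5 ties the baseline for the normal/abnormal interpretation shift table to readings taken before the first dose.

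**The concern.** The rule for untimed records assumes that whatever is scheduled on the first dose date happens before the dose. That is reasonable for date-only items, but not for ECGs, because the same SAP names a scheduled post-dose ECG on that date. Section 8 makes no exception for a record whose own label says post-dose.

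Two consequences follow for an untimed record of this kind. It becomes eligible as the baseline from which every later QTcF, PR, QRS and heart rate change is measured. It also stops being a post-baseline observation, so it cannot contribute to the worst post-baseline value in the categorical tables. The restriction to readings before the first dose covers only the interpretation shift table, not the numeric baseline. Heart rate is clearly of interest in this trial: bradycardia is the one grouped adverse event term that Section 5.6.2.4 spells out.

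**Working it through.** The SAP gives no figure to reproduce. The check applies the Section 8 rule to the Cycle 1 Day 1 ECGs and then evaluates the Table 5 criteria.

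**Step 1: which records are affected.** Screening is taken to fall before the first dose date.

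| Predose ECG | Post-dose ECG | Result under Section 8 |
|---|---|---|
| timed | timed | correct: predose is baseline |
| untimed | timed | correct: post-dose falls after the dose |
| timed | untimed | both pre-treatment; in nominal order the post-dose reading is last |
| untimed | untimed | both pre-treatment on one date, with no tie-break by clock; baseline ambiguous |
| not done | untimed | post-dose is pre-treatment and later by date than screening, so it is the baseline |

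Only an untimed post-dose record causes trouble. If the two Day 1 readings were treated as multiple values at one visit, the Section 8 averaging convention would give a mixture of the two.

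**Step 2: effect on the change.** Let P be the predose value, D the Day 1 post-dose value and W the later worst value.

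- Change from the predose baseline: W − P.
- Change from the post-dose baseline: W − D = (W − P) − (D − P).
- Change from the averaged baseline: (W − P) − (D − P)/2.

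The error is therefore the whole Day 1 shift, or half of it if averaged. Change is understated when D has moved in the same direction as W, and overstated when it has moved the opposite way.

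**Step 3: illustration against Table 5.** All ECG values are assumed, because the SAP gives none.

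Heart rate, P = 64, W = 47 bpm. From predose: (64 − 47)/64 = 26.6%, which meets the criterion of more than 25% to below 50 bpm.

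| D (bpm) | Post-dose baseline | Averaged baseline |
|---|---|---|
| 60 | (60 − 47)/60 = 21.7%, missed | (62 − 47)/62 = 24.2%, missed |
| 56 | (56 − 47)/56 = 16.1%, missed | (60 − 47)/60 = 21.7%, missed |
| 52 | (52 − 47)/52 = 9.6%, missed | (58 − 47)/58 = 19.0%, missed |

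QTcF, P = 420, W = 485 msec. From predose: 485 − 420 = 65 msec, which meets the criterion of more than 60 msec.

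| D (msec) | Post-dose baseline | Averaged baseline |
|---|---|---|
| 425 | 60, falls to the >30 to 60 row | 62.5, still >60 |
| 430 | 55, falls to the >30 to 60 row | 60, falls to the >30 to 60 row |
| 440 | 45, falls to the >30 to 60 row | 55, falls to the >30 to 60 row |
| 460 | 25, in neither change row | 45, falls to the >30 to 60 row |

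In every QTcF case the later 485 msec is still counted in the >480 to 500 msec row, which does not use baseline.

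**The case against.** The strongest reply is that the rule may never be triggered. Timed records are classified correctly, these are central triplicate ECGs taken at defined timepoints, and nothing in the SAP suggests that their times are missing. The fallback is a generic convention that suits date-only data. Section 5.6.5.2 already separates predose from post-dose by nominal timepoint, and Sections 8 and 9 leave further derivation rules to programming specifications that are not at hand. Where both Day 1 ECGs exist, only the nominal label can place the post-dose reading last, and that label also shows it to be post-dose. A programmer would have to use the label for ordering and ignore it for classification.

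Much of this stands. It limits the reach to untimed records of unknown number, and where a predose ECG exists it makes the baseline ambiguous rather than certainly wrong. It does not remove the point. Section 8 states a definite rule that gives the wrong class for these records, and unseen specifications do not correct a contrary rule in the SAP. Where the predose ECG was not done, date alone makes the post-dose reading the last eligible value, without any use of the label.

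A reader might infer that the rule hides the drug's cardiac effect. The documents do not support that: later readings are still counted against the absolute QTcF limits, and all ECG data and abnormalities are listed. A reader might also infer that the post-dose ECG is a 3-hour reading in all subjects. The 3-hour label follows Cycles 2 to 4, the central Cycle 1 ECGs are stated for Phase 2 subjects, and Phase 1 Holter data fall under a separate plan (Section 5.6.5.1).

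**Conclusion.** The point holds as a minor defect in a data-handling rule. Read literally, Section 8 allows an untimed, scheduled post-dose ECG on the first dose date to serve as the numeric baseline, or leaves the baseline ambiguous, and removes that reading from the post-baseline worst value. The change-from-baseline rows of Table 5 for QTcF, PR, QRS and heart rate could then be distorted for the subjects concerned. An absolute QTcF row could also lose a subject whose worst reading was that Day 1 ECG.

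The size cannot be stated. It depends on how many such records lack a time, which the SAP does not give and which may be zero. The direction is conditional too: change is understated only if the post-dose reading already reflects a drug effect in the same direction as later readings. The worked values are assumed and show that categories can change, not how often they would. No efficacy analysis is affected by this ECG problem.

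**What to change.** Add one sentence to Section 8: *When time is missing, the nominal timepoint governs; assessments scheduled post-dose on the first dose date are post-treatment.* Keep the present rule for scheduled assessments that are nominally predose or have no nominal timepoint, and check that the programming specifications say the same.

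The cost is one sentence. The nominal timepoint is already needed for averaging the triplicates in Section 5.6.5.2, so no new data are required.
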